4.1.2 Sub-Study 3 Outpatient Hospital Workers

1. Healthcare workers will enroll in stations in the ED.
2. Delegated and credentialed clinical investigator sends consent via email/DocuSign and reviews consent form with the participant
3. Conducts e-consent process with the patient and documents via telemedicine/DocuSign
4. If a participant is a member of the PATCH study team, then they are counselled to ensure they do not reveal their own participation during the consenting of participants to Sub-study 1.
5. Eligibility checklist is reviewed and signed by an appropriately delegated and credentialed clinical investigator

The PATCH Trial

6. Participant is randomized by IDS
7. Sub-Investigator orders study drug and PCR test.
8. Nasopharyngeal swab for COVID19, and blood collection if available/possible is performed in the designated area
9. A baseline ECG (6 lead ECG is acceptable) will be obtained if the participant has not had one recently. If the participant has had an ECG in the last 6 months, and they have not started any QT prolonging medications in the interim, the previously obtained ECG can be used.
10. Blinded study drug and 5 oral fluid collection kits are provided to the participant by Study member who reviews dosing of study drug (three pills daily) with the participant.

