Clinical Symptom monitoring: Appropriately delegated and credentialed study team members (as example: CRC) will screen for symptoms 1X per week and if present will document the likely treatment related AEs. Follow up with an appropriately delegated and credentialed physician investigator will be undertaken for assessment and grading of events. Participants will be asked if there have been changes in vision such as distortions of blurred vision. Patients who develop COVID-19 symptoms will be instructed to go to occupational health for nasopharyngeal swab. The rate of conversion to PCR positive in each arm at the 2-month mark will be used to assess the primary endpoint.

Electrocardiogram Recordings: An electrocardiogram (12 lead or 6 lead) will be recorded at baseline prior to the initiation of the study drug. Those participants with an ECG in the last 6 months and no QTc prolonging medications do not need a repeat baseline ECG. One month after starting the study drug a repeat ECG will be performed to confirm excessive QTc prolongation has not occurred. If the QTc has prolonged to >500ms dose reduction as described below will be attempted to achieve a QTc of <500ms. Due to the long half-life of HCQ, study medication can be started before the baseline ECG is read.

Pill diary: Electronic pill diary will be turned in by the participant at the end of the study.

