Oral fluid collection: Participants will be asked to collect oral fluid using the RNAPro-Sal collection kit manufactured by Oasis Diagnostics (<https://4saliva.com/products/rnapro-sal/>). These kits will be provided to the participant with the drug supply. The participant will have clear instructions on how to collect oral fluid on themselves. This process consists of inserting the gauze tip in the mouth for 4 minutes, removing and pushing the syringe to squeeze the fluid into the container. A video will be sent to the participant's email address and texted to them providing visual instructions on use. Participants should produce an early morning saliva sample from the posterior oropharynx (ie, coughed up by clearing the throat) before tooth brushing and breakfast, because nasopharyngeal secretions move posteriorly and bronchopulmonary secretions move by ciliary activity to the posterior oropharyngeal area while the patients are in a supine position during sleep. Participants will be instructed to collect oral fluid at the following time-points in the containers provided (before taking the first dose of study and every 2 weeks after that). The collected oral fluid should be placed in the freezer in a sealed container. This container will be collected after the participant is at the end of their participation. The participant will then wipe the container surface with disinfectant and return to site. If the participant becomes quarantined or hospitalized with COVID-19, a primary contact for the participant will be contacted and if asymptomatic and/or COVID-19 negative the driver will pick up the saliva using the same procedure.

8.5 Hydroxychloroquine Dose Reduction.

In outpatient arms 1 and 3, any AE of \geq Grade 2 or adjusted QTc prolongation to >500ms and attributed as possibly, probably or definitely related solely to HCQ will result in dose holiday and/or dose reduction of HCQ as described in Table 5. No more than 1 dose reductions are allowed.

Table 3: Hydroxychloroquine Dose Reduction Schema

Sub-Study	Dose mg/day	First dose reduction
1	400 mg twice daily	400mg daily
3	600 mg daily	400 mg daily

- If the second dose reduction is not tolerated, then the patient should discontinue the treatment.

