9.0 SCHEDULE OF EVENTS

Table 4. Schedule of events for sub-study 1			
	Before treatment	During treatment	Day of release from quarantine
Eligibility checklist	X		
Temperature (patient obtained)		Twice daily	X
COVID-19 symptom score		Daily	
Mobile Cardiac Telemetry	X	Daily	X
AE assessment, triage		Daily as needed	X
SARS-COV-2 PCR nasopharyngeal swab	X		
SARS-COV-2 PCR nares swab ¹	X	D3, D7	X (if ≤7 or 10 days, per CDC guidelines)
Oral fluid collection ²	X	D3, 7	X
TREATMENT			
Hydroxychloroquine or placebo		Twice every day	Return electronic diary

1- The nares swab before treatment sample can be performed at any time of day and should be collected before any study medication has been taken.

The PATCH Trial

2-For oral fluid collections, these should be performed in the morning to maintain consistency. For the before treatment collection, if HCQ is received during the day, there should not be a delay in starting HCQ in order to collect morning oral fluid. Instead study medication should be started and the next morning the first sample can be collected and considered the baseline sample. The timing of collection should be recorded in the daily diary.

Table 6. Schedule of events for Sub-study 3			
	Baseline / Pre-RX	During 2 months	End of 2 months
Eligibility checklist	X		
COVID-19 symptom score	X	Weekly	
AE check by telephone		1X/week	X
PCR SARS-COV-2 ¹	X	One month	X ²
Oral fluid collection	X	Every 2 weeks	X
Research Blood ²	X	One month	X
6 or 12 Lead Electrocardiogram	X	One month	
TREATMENT			
Hydroxychloroquine or placebo		3 pills daily	

- 1- this testing is dependent on availability of the test kits and can be deferred if test kits or testing capacity are not available
- 2- End of 2 months or at the time of symptom progression 3- one 10-mL tiger top serum separator tubes (SST). This collection can be deferred to accommodate the conditions of the COVID-19 crisis situation and how it affects resources and health care worker schedules.
- 3- If subject has had an EKG in the last 6 months the baseline EKG can be deferred. Since this EKG is for research purposes only, the serial EKGs can be deferred to accommodate the conditions of the COVID-19 crisis and how it affects resources and health care worker schedules.

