Once the subject has completed 2 months the person is off study.

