Upon completion of the trial and the necessary data cleaning, the dataset will be locked for final analysis. This may occur at the final sample size of N=200, or earlier in the case of a decision to halt for futility. This final analysis will be conducted by study staff under supervision of the PIs with full involvement of two study statisticians. PIs and statisticians will review all results and p-values before analysis is determined complete and before manuscript submission.

Analysis Set	Definition	Outcomes
Randomized patients	Any patient randomized	Demographics
Evaluable for primary outcome	Randomized covid-19 negative at baseline and took at least one dose of study drug, and either completed all study procedures or	Primary outcome
Evaluable for Safety	Randomized and took one dose of study drug	Adverse events
Evaluable for drug-induced QTc prolongation	Randomized COVID-19 negative at baseline, took at least one dose of study medication and had a baseline and one month EKG	Change in QTc
Evaluable for antibody prevalence	Subjects who had blood drawn at specified timepoint	Antibody prevalence

Missing Data

Missing data values will not be imputed. Only observed values will be used for data analysis and presentation.

Subject Disposition

The summary statistics of the subjects will include the following information:

- The number and percentage of subjects who complete the trial and who drop out before trial completion according to the treatment groups.
- The number and percentage of subjects per analysis population according to the treatment groups.

Protocol Deviations

All protocol violations will be listed. The sponsor and/or its designee will review the protocol violations before the database is locked, and determine whether the involved subjects will be excluded from the per protocol set.

Demographic and Baseline Variables

The following demographic and baseline variables collected prior to the start of study medication will be summarized by treatment group.

Sex

Age

Profession (MD, nurse, respiratory technician, etc)

Location of work (ICU, ward, emergency department, etc)

Past medical history

Baseline testing will include NP swab testing for SARS-CoV-2, serologic testing for antibodies against SARS-CoV-2, and ECG testing (protocol amended DATE to include as a baseline test).

Adverse event reporting

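### The Table 6 footnote lets Sub-Study 3's one-month ECG be deferred with no latest date, although section 8.4.2 makes it a QTc safety check

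*Protocol*

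**What the plan says.** Protocol section 8.4.2 (Electrocardiogram Recordings) gives the repeat ECG a safety purpose: "One month after starting the study drug a repeat ECG will be performed to confirm excessive QTc prolongation has not occurred". If the QTc exceeds 500 ms, it directs that dose reduction be attempted. Section 8.5 supplies the rule: "adjusted QTc prolongation to >500ms and attributed as possibly, probably or definitely related solely to HCQ will result in dose holiday and/or dose reduction".

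Table 6 in section 9.0 schedules the Sub-Study 3 ECG at baseline and at one month, with nothing in the end-of-2-months column. The footnote on these ECGs (the second item numbered 3 under the table) reads in part: "Since this EKG is for research purposes only, the serial EKGs can be deferred to accommodate the conditions of the COVID-19 crisis". It goes on to mention resources and staff schedules. It states no maximum delay and no rule for a missed ECG.

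The conditions for skipping the baseline ECG also differ. Section 4.1.2, step 9, adds a medication condition: "If the participant has had an ECG in the last 6 months, and they have not started any QT prolonging medications in the interim". Section 8.4.2 agrees in substance: "Those participants with an ECG in the last 6 months and no QTc prolonging medications do not need a repeat baseline ECG". The footnote asks only for an ECG in the last 6 months.

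The SAP's amendment table lists QTc change as a new secondary endpoint. Its analysis set is COVID-19-negative randomized participants who "took at least one dose of study medication and had a baseline and one month EKG". On missing data the SAP says: "Missing data values will not be imputed".

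**The concern.** One part of the protocol uses the ECG to protect participants, while another calls it research and gives that as the reason it can wait. Staff who work from the schedule of events could follow the footnote in good faith and postpone the ECG past the point where its result can change dosing.

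Participants take 600 mg daily for 2 months, and section 7.3 itself states that HCQ can prolong the QT interval. The other safeguards lower the risk but do not measure QTc: weekly adverse event calls, cardiac exclusions, a list of excluded QTc-prolonging drugs, and consultation before new medication. Mobile telemetry is described only for Sub-Study 1. The baseline ECG gives limited cover, because Sub-Study 3 entry sets no QTc cut-off and drug may start before that ECG is read.

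At stake are timely detection of a QTc above 500 ms without symptoms and, secondarily, the completeness of the QTc analysis.

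**Working it through.** The plan gives no figure to reproduce. The check compares the texts and then counts days.

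**Side by side**

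| Question | Section 8.4.2, with 8.5 | Table 6 ECG footnote |
|---|---|---|
| Purpose of the one-month ECG | Rule out excessive QTc prolongation | Research only |
| Is it due? | Will be performed at one month | Deferrable for crisis conditions, resources or staff schedules |
| Latest date | One month stated | None |
| Consequence | Above 500 ms leads to dose reduction; 8.5 adds dose holiday | None stated |

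The word *research* could simply mean that the study, not clinical care, ordered the ECG. That would not stop anyone acting on the result. But the footnote uses the label as its ground for deferral, and that ground is at odds with the purpose in 8.4.2.

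**Number of scheduled on-treatment QTc measurements.** In Sub-Study 3 there is one, the one-month ECG in Table 6.

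**Time left to act.** Inputs: eight weeks of study medication (SAP, Study Design), so 8 × 7 = 56 dosing days. One month is taken as day 28, matching the SAP's 4-week visit. Days left = 56 − day of ECG.

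- Day 28: 56 − 28 = 28 days, 28/56 = 50%
- Day 42: 56 − 42 = 14 days, 14/56 = 25%
- Day 56: 56 − 56 = 0 days, 0%

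If the protocol's 2 months is read as 61 days (an assumption), day 28 leaves 61 − 28 = 33 days (54%) and day 42 leaves 61 − 42 = 19 days (31%).

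**End of follow-up.** Section 10.3 states: "Once the subject has completed 2 months the person is off study". An ECG deferred to that point can still be recorded, but it can no longer lead to a change in study dosing.

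**The case against.** The strongest reply is that the footnote postpones the ECG and does not waive it. Section 8.4.2 still says it will be performed, Table 6 places it during the 2 months, and deferral is tied to stated causes. That stands. A reader might infer that the plan permits no on-treatment ECG at all, or deferral for any reason. The text does not go that far; it lacks only a latest date.

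Four further limits also stand.

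- Section 8.5 never names the one-month ECG. It sets a QTc trigger, and 8.4.2 makes the link. Unscheduled ECGs are not barred and could also feed the trigger, so only the scheduled input is at risk.
- A reader might infer that anyone with a deferred ECG drops out of the SAP's QTc analysis. The SAP defines no window for the one-month ECG, so that loss is certain only if no ECG is done. Whether a late one counts is unstated.
- The fuller baseline-waiver condition appears twice elsewhere and still applies. The footnote merely abbreviates it.
- The day counts are calendar subtraction. The protocol stresses HCQ's long half-life, so exposure does not end with dosing. This limits what the counts measure, but it gives no reason to leave the date open: a late dose change has less time to take effect.

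The reply does not remove the central conflict. A safety check with a stated dosing consequence should not be deferrable without limit on the ground that it is research.

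**Conclusion.** The concern holds as a conflict in the current protocol text. If the one-month ECG is deferred to the end of dosing, the QTc rule has no scheduled input for that participant while the dose can still be changed. The time in which to act falls from 28 of 56 days at day 28 to none at day 56.

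This assumes that dosing lasts eight weeks and that one month means about day 28. A reader might infer that participants were harmed or that prolongation went undetected. The documents do not support this: they give no deferral rate, no rate of QTc above 500 ms and no harm estimate. The primary analysis, alpha and power are unaffected. The change is worth making because it is cheap and bears on safety, but it does not call the efficacy design into question.

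**What to change.** Delete the research-only reason from the Table 6 footnote and replace the footnote with text such as:

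*A baseline ECG from the last 6 months may be used if no QT-prolonging medication has been started since. The one-month ECG (6 or 12 lead) is a safety assessment under 8.4.2, targeted at about day 28. It may be deferred for crisis conditions but must be done while the participant is still taking study drug, and by day 42. If none is recorded by then, study drug is held until an ECG is obtained, unless a clinical or cardiology sub-investigator documents a reason to continue.*

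Day 42 is a judgement. It allows 42 − 28 = 14 days of deferral and leaves 14 of 56 dosing days. Another fixed date during dosing would also serve, with less time to act the later it falls.

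In the SAP, define the one-month EKG for the QTc analysis set as any on-treatment ECG from about day 21 to the end of dosing, and report its study day. The analysis window is deliberately wider than the safety deadline so that early or late ECGs are not dropped.

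The cost is one footnote and one SAP line, slightly less scheduling flexibility, and a brief review for each participant without an ECG by the deadline. No new test or staff is needed. The absence of a QTc entry cut-off and the start of drug before the baseline ECG is read are separate choices that this change leaves as they are.

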10.0 MEASUREMENT OF EFFECT

10.1 Definitions

Evaluable for toxicity. All participants will be evaluable for toxicity from the time of their first treatment with HCQ or placebo.

Evaluable for primary outcome: Participants who received at least one dose of study drug will be evaluable for the primary outcome as long as they meet the following status for SARS-COV2 PCR: sub-study 1: PCR+ Sub-study 3: PCR negative.

10.2 Response Criteria

Sub-Study 1: Time to release from quarantine. The criterion is afebrile for 72 hours AND improvement of symptoms AND at least 7 or 10 days have passed since symptoms started (according to contemporary CDC guidelines). To quantitatively assess improvement of symptoms the grading system in Section 8.5 will be used.

The PATCH Trial

May 2020. There was a change in CDC guidelines on quarantine time following onset of symptoms, changing from 7 to 10 days. We have adopted the new guidelines, but some of the earlier patients enrolled in the study were released in a shorter time than they would have been under the new guidelines. Because the response is time to release, we will record both release dates for each patient. While the release based on 10 days will be the primary outcome, we will run a parallel analysis of the 7-day measure as part of a sensitivity analysis.

Sub-Study 3: Measurement of SARS-CoV-2 positivity defined by PCR. Time to infection will be defined as the time in days from enrollment on the study to time to COVID-19 symptoms.

10.3 Off treatment/Off Study

Each participant has the right to withdraw from the study at any time without prejudice. The investigator may discontinue any person's participation for any reason, including adverse event or failure to comply with the protocol. Should a participant withdraw from the study, the reason(s) must be stated on the case report form, and a final evaluation of the participant should be performed. Reasons for withdrawal include the following:

Progression of Disease: Remove participant from protocol therapy at the time progressive disease is documented. Progression of disease is left to the discretion of the treating physician/ sub-Investigator; however, the following guidelines are provided to help decision making for discontinuing study drug:

Sub-study 1: Progression of disease can be confirmed if there is increase in COVID-19 symptom score for 2 days in a row and is three points higher than baseline. Once criteria for release from quarantine is met in SS1 the patient is off study. Once the person is hospitalized for COVID-19 in sub-study 1 the subject is off study. Participants who have progressive symptoms and are subsequently hospitalized as related to COVID-19 will not be crossed over to receive HCQ at the time of unblinding.

Sub-study 3: Development of new symptomology consistent with COVID-19: e.g. fever, cough, shortness of breath and SARS-COV2 test positivity would lead to unblinding. If on placebo the subject can crossover to HCQ for treatment and stay on study for 14 days or release from quarantine. If the subject was on HCQ the subject is off study and will be instructed to seek medical attention through their primary care physician

Extraordinary Medical Circumstance: If at any time the treating physician feels constraints of this protocol are detrimental to the participant's health remove the participant from protocol therapy.

Participant's refusal to continue treatment: In this event, document the reason(s) for withdrawal.

Failure to comply with protocol (as judged by the investigator such as compliance below 80%, failure to maintain appointments, etc.).

Withdrawal from treatment per patient choice: Patients may withdraw from study treatment at any point in the study for any reason. These subjects are allowed to withdraw from treatment but continue to participate with any of the other study procedures for the intended 2 month period.

Delay in treatment > 7 days due to toxicity

Once the subject has completed 2 months the person is off study.

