2.0 OBJECTIVES

2.1 PRIMARY OBJECTIVES

Sub-Study 1 (home quarantined COVID-19 patients): Median time to release from quarantine by meeting the following criteria: 1) No fever for 72 hours without the use of fever-reducing medication 2) improvement in other symptoms and 3) 7 or 10 days have elapsed since the beginning of symptom onset, depending on CDC guidelines at the time. (Outcomes based on 7 and 10 days will be constructed for each subject.)

The first date of quarantine will be considered the date of SARS-CoV-2 nasopharyngeal swab test that confirmed positivity.

Sub-Study 3 Healthcare worker prophylaxis: Rate of COVID-19 infection at 2 months

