1.2 SECONDARY OBJECTIVES

Sub-Study 1: Rate of participant-reported secondary infection of housemates, rate of hospitalization, rate of treatment related adverse events

Sub-Study 3: rate of treatment related adverse events

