8. Appropriately delegated and credentialed study team member calls the participant and reviews use of the study drug, establishes best contact information for response monitoring (See Section 8.5), and asks the patient to connect/wear the cardiac telemetry monitoring device. If the baseline, adjusted (Pre-treatment) Qtc is >500 , the patient will be removed from the study and advised to go to the emergency room for admission to the hospital for evaluation for inpatient monitoring. Since the half life of HCQ is many days, the activation of the ZioAT and transmission of the baseline QTc does not need to occur before starting study medication.

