Anterior nares specimen: Participants will self-collect these samples on day 0 (start date for HCQ) before the HCQ is taken, Day 3, and day 7

The PATCH Trial

Foam swab provided: Puritan 6" Sterile Standard Foam Swab w/ Polystyrene Handle (SKU # 25-1506 1PF)

Collection instructions: Use a single foam swab for collecting specimens from both nares. Insert foam swab into 1 nostril straight back (not upwards). Once the swab is in place, rotate it in a circular motion 2 times and keep it in place for 15 seconds. Repeat this step for the second nostril using the same swab. Remove foam swab and insert the swab into the supplied tube.

Storage instructions: The collected swab should be placed into the bag marked "Nares swabs collected" and the date and time of the swab collection should be filled out Redcap. The "Collected" bag is then placed in the freezer in the same sealed container as the oral fluid.

Specimen stability for all specimen types for all tests is now as follows:

Room temperature: 5 days

Refrigerated (2 °C–8 °C): 5 days

Frozen (-20 °C): 7 days

Frozen (-70 °C): Acceptable

Specimen pickup: At the end of quarantine, or end of study procedures, the nares swabs will be collected. And shipped to Quest Diagnostics to assess viral titers. Cold packs or dry ice should be used during collection and cold packs should be used during shipping to Quest.

Pill diary: When the participant is released from quarantine the electronic pill diary must be submitted electronically.

Monitoring co-inhabitants: Appropriately delegated and credentialed study team members (as example: Clinical Research Coordinator) will ask the participant about the status of co-inhabitants daily to 14 days after the quarantine is completed to determine if the participant's co-inhabitants did or did not have symptoms or tested positive for COVID-19.

8.4.2 Sub-Study 3:

SARS-CoV-2 testing: Hospital workers will be tested for SARS-CoV-2 virus by RT-PCR every month. This will be a nasopharyngeal swab that will be processed by Quest diagnostics performed during enrollment at one month and two months. This screening NP swab will provide results in EPIC for clinical action within 72 hours. Eligibility criteria to start study medication does not require a negative PCR result to return.

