Given the median duration of viremia is 14-20 days in mild cases, we will assume the null hypothesis that in the placebo cohort the median time to release from quarantine is 10 days from receiving a positive test. In order for HCQ to be considered more effective in this treatment setting we aim to see a median time to release from quarantine of 5 days. These values correspond to daily hazard rates of 0.069 and 0.139 respectively. We will randomize 1:1 HCQ to control and with 100 patients with 50 in the placebo arm and 50 in the HCQ arm. The one-sided z- test (alpha=.05) will have an overall 95% power to detect a significant difference between the two groups with medians of 10 and 5 days.

Based on the new CDC guidelines for quarantine release we will modify the analysis as follows: Given the median duration of viremia is 14-28 days in mild cases, we will assume the null hypothesis that in the placebo cohort the median time to release from quarantine is 14 days from receiving a positive test. In order for HCQ to be considered more effective in this treatment setting we aim to see a median time to release from quarantine of 7 days. These values correspond to daily hazard rates of 0.048 and 0.094 respectively. We will randomize 1:1 HCQ to control and with 100 patients with 50 in the placebo arm and 50 in the HCQ arm. The one-sided z- test (alpha=.05) will have an overall 93% power to detect a significant difference between the two groups with medians of 14 and 7 days.

The *hypothesis* will be tested using a one-sided test, with a z-score corresponds to the log of the hazard-ratio for recovery between the two groups. We will obtain estimates of the hazard ratio and group median survival, and 95% CI, from Cox regression. As a secondary analysis, we will stratify the analysis, and obtain separate estimates of the hazard-ratio by group. However, we are not powered to test the interaction for significance, and we do not expect significance within group.

Given that 20 subjects were recruited and treated under the old CDC guidance, we will conduct a primary analysis based on the updated 10-days from onset criterion. For the subjects who were released under the old criterion, this number will be constructed by assessing when a patient would have been released under the new rules. We will follow that with additional secondary analyses to assess the sensitivity of the results to the change in

The PATCH Trial

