In addition, at our second interim analysis for SS3, we will evaluate the conditional power based on our original assumptions. The actual effect size for this study is completely unknown. If the effect size is smaller than we anticipated but still promising, and our conditional power falls between 0.5 and 0.8, we will consider formally adjusting the sample size in SS3 to achieve a conditional power of 0.8 based on an updated understanding of the effect size (29).

Z-Value Boundaries			
	Boundaries		Information
Stage	Efficacy	Futility	Proportion
1	2.9473	-1.2318	0.2500
2	2.5825	-0.2676	0.5000
3	1.6664	1.6664	1.0000

P-Value Boundaries			
	Boundaries		Information
Stage	Efficacy	Futility	Proportion
1	0.00160	0.89099	0.2500
2	0.00491	0.60550	0.5000
3	0.04782	0.04782	1.0000

12.2 Analysis of Secondary Endpoints.

Secondary outcomes will at least be analyzed as summary statistics, with group means, odds-ratios, and 95% CIs. We may conduct exploratory analyses using regression methods appropriate for each type of measure.

Sub-Study 1: Rate of secondary infection of housemates is a binomial count by household. We will summarize the proportion or rate by group, with 95% CI. With sufficient data, we will explore subgroups, patient, and secondary patient characteristics using logistic regression. Rate of hospitalization is a binary measure. We will summarize rates by group, and estimate the odds-ratio for treatment. Adverse event rates will be summarized as a count by subject, and mean count by group, and we will estimate a rate-ratio for treatment.

Sub-Study 3: For hospital employees, Adverse event rates will be summarized as a count by subject, and mean count by group, and we will estimate a rate-ratio for treatment.

REFERENCES

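### Sub-Study 1 sets no common observation window for hospitalization: scheduled follow-up ends at release, the primary outcome, so the odds ratio can be biased towards the arm released sooner

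*Protocol*

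**What the plan says.** The Sub-Study 1 primary outcome is time to release (protocol 2.1: "Median time to release from quarantine by meeting the following criteria"). The secondary objectives in 1.2 are "Rate of participant-reported secondary infection of housemates, rate of hospitalization, rate of treatment related adverse events", with no time frame for any of them. The analysis in 12.2 reads: "Rate of hospitalization is a binary measure. We will summarize rates by group, and estimate the odds-ratio for treatment". It mentions no window, person-time or competing event. The SAP covers Sub-Study 3 only and adds nothing here.

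Follow-up of the participant ends at release in several places. Section 10.3 states "Once criteria for release from quarantine is met in SS1 the patient is off study". The last column of Table 4 (Section 9.0) is the day of release. Section 7.4 stops HCQ then at the latest, and Section 11.0 closes the adverse event reporting period at the last dose.

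Contact itself goes on. Under 8.4.1 the team "will ask the participant about the status of co-inhabitants daily to 14 days after the quarantine is completed", but the stated purpose is to learn about the housemates.

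**The concern.** A yes/no outcome compared by odds ratio assumes that each participant had the same opportunity to be counted. Here the scheduled opportunity lasts until release, and release is what the treatment is meant to bring forward. For HCQ, 13.1 says "we aim to see a median time to release from quarantine of 7 days", against 14 days on placebo. Ascertainment of the secondary outcome is thus tied by rule to the primary outcome.

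If HCQ shortened quarantine without changing late deterioration, admissions after release would drop out of the count more often in the HCQ arm. Drug exposure does not end at release either: step 8 of 4.1.1 says "Since the half life of HCQ is many days". A lower admission rate on HCQ could then partly reflect shorter observation and be taken for benefit.

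**Working it through.** **The plan's own figure.** No figure is stated for hospitalization. Section 13.1 gives 93% power for the primary outcome at medians of 14 and 7 days, 50 per arm, one-sided alpha 0.05. With λ = ln2/median, λ is 0.0495 per day (placebo) and 0.0990 per day (HCQ). For a hazard-difference test with 50 events per arm, information = 1/(0.0495²/50 + 0.0990²/50) ≈ 4,080, z = 0.0495 × √4,080 ≈ 3.16, and power = Φ(3.16 − 1.645) ≈ 93.5%. The stated power reproduces and is not in dispute. (The hazards printed in 13.1, 0.048 and 0.094, differ slightly from ln2/14 and ln2/7; they give about 92%.)

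**Length of observation.** Up to day 28, mean time to release, ignoring admissions, is (1 − e^(−28λ))/λ:
- placebo: 0.75/0.0495 = 15.1 days
- HCQ: 0.9375/0.0990 = 9.5 days

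**Model for admissions.** These are assumptions, not figures from the documents: constant release hazard λ; the same admission hazard h = 0.005 per day before release in both arms; hazard f × h after release; a 28-day horizon.

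*Count to release, capped at day 28:* risk = h/(h+λ) × (1 − e^(−28(h+λ))).
- placebo: 0.0917 × 0.783 = 7.2%
- HCQ: 0.0481 × 0.946 = 4.5%
- odds ratio = (0.0455/0.9545)/(0.0718/0.9282) = 0.62

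*Full 28-day count, whatever the release date:* risk = 1 − e^(−28(h+λ)) − λe^(−28fh) × (1 − e^(−28(h+λ−fh)))/(h+λ−fh).

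| f | Placebo | HCQ | Odds ratio, full count | Share of 28-day admissions after release, placebo v HCQ |
|---|---|---|---|---|
| 0 | 7.2% | 4.5% | 0.62 | 0% v 0% |
| 0.25 | 8.7% | 6.8% | 0.76 | 18% v 33% |
| 0.5 | 10.2% | 8.9% | 0.86 | 30% v 49% |
| 1 | 13.1% | 13.1% | 1.00 | 45% v 65% |

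The count to release gives 0.62 in every row. The bias is the gap between 0.62 and the full-count odds ratio: none at f = 0, and growing with f. For h from 0.002 to 0.01 the count to release gives 0.61 to 0.62, and the full count 0.75 to 0.77 (f = 0.25), 0.86 to 0.87 (f = 0.5) and 1.00 (f = 1).

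**Sensitivity to the release model.** A constant hazard allows release from day 0, which the release criteria prevent for most participants. With a 6-day minimum and the same medians, the capped count to release gives about 0.46, against 0.66 (f = 0.25) and 1.00 (f = 1). The pattern is unchanged.

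**Precision.** At the capped rates, 50 per arm gives about 3.6 v 2.3 admissions. The standard error of the log odds ratio is √(1/3.6 + 1/46.4 + 1/2.3 + 1/47.7) ≈ 0.87, so the approximate 95% interval around 0.62 is 0.11 to 3.4.

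**The case against.** **Collection does not plainly stop at release.** A reader of 10.3 might infer that later admissions are never collected and later harm is missed. The documents do not support that. Section 11.1 requires adverse events to be sought at each contact, and the housemate calls are contacts. Section 11.1.1 collects all serious events after consent, related or not, with no calendar end for the individual. Section 11.1 also has later serious events recorded if at least possibly related, and 11.0 asks participants to report later events thought related. A serious drug-related arrhythmia after release would fall within these rules.

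This stands against the strong reading but does not supply the odds ratio. The route conflicts with the off-study rule and the reporting period. Much of it is unscheduled or filtered by relatedness, and 11.1.1 itself limits reporting after its collection periods to events believed related. The text on hospitalization that follows 11.1.1 exempts admissions for the target disease unless judged a worsening, so COVID-19 admissions may be left out. No section feeds later admissions into the 12.2 comparison.

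**The bias is conditional.** It needs admissions after release and release times that differ by arm. Release requires 72 hours without fever, improved symptoms and 7 or 10 days from onset (10.2), so later risk may be low; the documents give no rate. The 7-day median is a target. If HCQ does not change release time, the windows do not differ by arm. This stands in full.

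**Importance is limited.** Hospitalization is one of three secondary outcomes, nowhere described as the main safety outcome, and 12.2 names no formal test for it. With so few events the interval would be very wide. This also stands and bears on weight, but a wide interval does not remove a bias built into the follow-up rule.

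**Conclusion.** The point holds in a conditional form. Sub-Study 1 defines no common window for hospitalization, and scheduled follow-up of the participant ends at the primary outcome. The odds ratio can therefore be biased towards the arm released sooner, given a difference in release times and some admissions after release.

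At the planned medians, with equal admission hazards before release and a 28-day cap, the odds ratio would be about 0.62 where a full count would show 0.76, 0.86 or 1.00, for a later hazard of a quarter, half or all of the earlier one. With no later risk, 0.62 is a real consequence of faster recovery and nothing is biased. The admission hazard, the fraction f and the 28 days are assumptions.

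A reader might also reach an odds ratio of 0.50 by counting to release without a time limit, since h/(h+λ) gives odds h/λ and 0.0495/0.0990 = 0.50. That figure should not be set against 28-day counts, because the horizons differ; like for like, it is 0.62.

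The plan should be changed because the remedy is cheap, but this is a matter of a secondary outcome and does not touch the primary analysis.

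**What to change.** - **12.2:** define hospitalization, and death, over one fixed window from randomisation (for example day 28) for every randomised Sub-Study 1 participant, whatever the release date. Compute the odds ratio on that window.
- **8.4.1:** add a question about the participant's own admissions to the daily calls that already run after quarantine. These calls alone do not equalise the windows, because their end moves with release: at the planned medians they would end near day 21 (7 + 14) on HCQ and day 28 (14 + 14) on placebo, counted from the positive test. Add one phone or chart check for everyone at the end of the fixed window.
- **10.3:** state that release does not end outcome follow-up. If death is counted, follow-up must also continue after a COVID-19 admission, which now takes the participant off study. Treatment rules need no change for this.
- **8.4.1, 10.3, 11.0, 11.1, 11.1.1 and the hospitalization text that follows it:** reconcile these so that it is clear which events after release are collected, for how long, and whether COVID-19 admissions count.

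The cost is a question on calls already made and one status check. Some participants will need a contact later than now planned.
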